8.2.3.2 Pulse Oximetry

Oxygen saturation will be measured using a standard pulse oximeter. The subject must be in a rested and calm state for at least 5 minutes before pulse oximetry assessments are completed.

8.2.3.3 Electrocardiograms (ECGs)

Subject must be in supine position in a rested and calm state for at least 5 minutes before ECG assessment is conducted. If the subject is unable to be in the supine position, the subject should be in the most recumbent position as possible. ECGs should be performed in a standardized method, in triplicate (where applicable), and run consecutively. Each triplicate, which consists of three 10-second tracings, should be completed within a total of five minutes from the start of the first to the completion of the third, prior to blood draws or other invasive procedures. Each ECG must include the following measurements: QRS, QT, QTc, RR, and PR intervals.

Triplicate ECGs (to be only performed if the dose being evaluated is higher than the MTD established in subjects with mCRPC [Study 20180101])

At pre-dose on cycle 1 day 1, baseline ECGs should be collected at 3 time points ≥ 5 minutes apart, with each baseline ECG performed in triplicate, and with at least

5 minutes between the end of each triplicate and the start of the next (total 9 ECGs). During cycle 1 and cycle 2 (at the time points per Schedule of Activities), each ECG should be performed in triplicate (total 3 ECGs). See Section 1.3 for ECG collection time points.

[figure not shown]
Safety ECGs

As listed in Section 1.3, single ECGs where applicable will be performed and will be referred to as safety ECGs.

The PI or designated site physician will review all ECGs. ECGs will be transferred electronically to an ECG central vendor per Amgen instructions. Once signed, the original ECG tracing will be retained with the subject's source documents. At the request of the sponsor, a copy of the original ECG will be made available to Amgen.

8.2.3.4 Vital Status

Vital status must be obtained for all subjects within the limits of local law. This includes subjects who may have discontinued study visits with or without withdrawing consent and should include interrogation of public databases, if necessary. If deceased, the date and reported cause of death should be obtained.

8.2.4 Adverse Events and Serious Adverse Events

The method of recording, evaluating, and assessing causality of adverse events, and serious adverse events and the procedures for completing and transmitting serious adverse event reports are provided in Section 11.4.

8.2.4.1 Time Period and Frequency for Collecting and Reporting Safety Event Information

8.2.4.1.1 Adverse Events

The adverse event grading scale to be used for this study will be the CTCAE and is described in Section 11.4. CRS, which will be graded using the criteria referenced in the publication by Lee et al (2014) (see Section 11.10.1) and TLS, which will be graded according to the Cairo Bishop criteria referenced in the publication by Coiffier et al (2008) (see Section 11.10.2), and ICANS will be using the criteria referenced in the publication by Lee et al (2019) (see Section 11.10.3).

The investigator is responsible for ensuring that all adverse events observed by the investigator or reported by the subject that occur after first dose of AMG 160 through the safety follow-up visit are reported using the Event CRF.

8.2.4.1.2 Serious Adverse Events

The investigator is responsible for ensuring that all serious adverse events observed by the investigator or reported by the subject that occur after signing of the informed consent through the **safety follow-up visit** are reported using the Event CRF.

All serious adverse events will be collected, recorded and reported to the sponsor or designee within 24 hours of the investigator's knowledge of the event, as indicated in Section 11.4. The investigator will submit any updated serious adverse event data to the sponsor within 24 hours of it being available.

The criteria for grade 4 in the CTCAE grading scale differs from the regulatory criteria for serious adverse events. It is left to the investigator's judgment to report these grade 4 abnormalities as serious adverse events.

8.2.4.1.3 Serious Adverse Events After the Protocol-required Reporting Period

If the investigator becomes aware of serious adverse events (including fatal events) after the protocol-required reporting period (as defined in Section 8.2.4.1.2) is complete, these serious adverse events will be reported to Amgen (regardless of causality). The investigator will report **these** serious adverse events to Amgen within 24 hours following the investigator's **awareness** of the event **on the Events CRF**.

After end of study, there is no requirement to actively monitor study subjects after the study has ended with regards to study subjects treated by investigator.

However, if the investigator becomes aware of serious adverse events suspected to be related to investigational product, then these serious adverse events will be

reported to Amgen within 24 hours following the investigator's awareness of the event.

Serious adverse events reported outside of the protocol-required reporting period will be captured within the safety database as clinical trial cases and handled accordingly based on relationship to investigational product.

If further safety related data is needed to fulfill any regulatory reporting requirements for a reportable event, then additional information may need to be collected from the subject's records if the subject ends the study.

8.2.4.1.4 Reporting a Safety Endpoint as a Study Endpoint

Safety endpoints (any fatal event occurring outside the protocol required reporting period) that are study endpoints are reported on the Event CRF. All endpoints that also meet the criteria of serious adverse event must also be transmitted to safety within 24 hours of the investigator's knowledge of the event (refer to Section 11.4).

8.2.4.2 Method of Detecting Adverse Events and Serious Adverse Events

Care will be taken not to introduce bias when detecting adverse events and/or serious adverse events. Open-ended and non-leading verbal questioning of the subject is the preferred method to inquire about adverse event occurrence.

8.2.4.3 Follow-up of Adverse Events and Serious Adverse Events

After the initial adverse event/serious adverse event report, the investigator is required to proactively follow each subject at subsequent visits/contacts. All adverse events and serious adverse events will be followed until resolution, stabilization, until the event is otherwise explained, or the subject is lost to follow-up (as defined in Section 7.3). Further information on follow-up procedures is given in Section 11.4.

All new information for previously reported serious adverse events must be sent to Amgen within 24 hours following knowledge of the new information. If specifically requested, the investigator may need to provide additional followup information, such as discharge summaries, medical records, or extracts from the medical records.

Information provided about the serious adverse event must be consistent with that recorded on the Event CRF.

8.2.4.4 Regulatory Reporting Requirements for Serious Adverse Events

If subject is permanently withdrawn from protocol-required therapies because of a serious adverse event, this information must be submitted to Amgen.

Prompt notification by the investigator to the sponsor of serious adverse events is essential so that legal obligations and ethical responsibilities towards the safety of subjects and the safety of a study treatment under clinical investigation are met.

The sponsor holding the relevant Investigational New Drug/Clinical Trial Application for either AMG 160 or ⁶⁸Ga-PSMA-11 has a legal responsibility to notify both the local regulatory authority and other regulatory agencies about the safety of AMG 160 or ⁶⁸Ga-PSMA-11, respectively, under clinical investigation. The sponsor will comply with country-specific regulatory requirements relating to safety reporting to the regulatory authority, IRBs/IECs, and investigators.

Individual safety reports must be prepared for suspected unexpected serious adverse reactions according to local regulatory requirements and sponsor policy and forwarded to investigators as necessary.

An investigator who receives an individual safety report describing a serious adverse event or other specific safety information (eg, summary or listing of serious adverse events) from the sponsor will file it along with the Investigator's Brochure and will notify the IRB/IEC, if appropriate according to local requirements.

8.2.4.5 Safety Monitoring Plan

Subject safety will be routinely monitored as defined in Amgen's safety surveillance and signal management processes.

8.2.4.6 Pregnancy and Lactation

Details of all pregnancies and/or lactation in female subjects and, if indicated, female partners of male subjects will be collected after the start of study treatment and until 4 months after the last dose of AMG 160.

If a pregnancy is reported, the investigator is to inform Amgen within 24 hours of learning of the pregnancy and/or lactation and is to follow the procedures outlined in Section 11.5. Amgen Global Patient Safety will follow-up with the investigator regarding additional information that may be requested.

Abnormal pregnancy outcomes (eg, spontaneous abortion, fetal death, stillbirth, congenital anomalies, ectopic pregnancy) are considered serious adverse events.

Further details regarding pregnancy and lactation are provided in Section 11.5.

8.2.5 Clinical Laboratory Assessments

Refer to Section 11.2 for the list of clinical laboratory tests to be performed and to the Schedule of Activities (Section 1.3) for the timing and frequency.

The investigator is responsible for reviewing laboratory test results and recording any clinically relevant changes occurring during the study in the Event CRF. The investigator must determine whether an abnormal value in an individual study subject represents a clinically significant change from the subject's baseline values. In general, abnormal laboratory findings without clinical significance (based on the investigator's judgment) are not to be recorded as adverse events. However, laboratory value changes that require treatment or adjustment in current therapy are considered adverse events. Where applicable, clinical sequelae (not the laboratory abnormality) are to be recorded as the adverse event.

All protocol-required laboratory assessments, as defined in Section 11.2, must be conducted in accordance with the laboratory manual and the Schedule of Activities (Section 1.3).

Pregnancy Testing

A high sensitive (serum) pregnancy test should be completed at screening and within 7 days of initiation of investigational product for females of childbearing potential.

Note: Females who have undergone a bilateral tubal ligation/occlusion should have pregnancy testing per protocol requirements. (If a female subject, or the partner of a male subject, becomes pregnant it must be reported on the Pregnancy Notification Form, see Figure 11-2). Refer to Section 11.5 for contraceptive requirements.

Additional pregnancy testing should be performed at monthly intervals during treatment with protocol-required therapies and 4 months after the last dose of protocol-required therapies.

[figure not shown]
Additional on-treatment pregnancy testing may be performed at the investigator's discretion or as required per local laws and regulations.

[figure not shown]
8.2.6 Pharmacokinetic Assessments

[figure not shown]
All subjects enrolled will have PK samples assessed.

Whole blood samples of approximately 2.5 mL will be collected for measurement of serum concentrations of AMG 160 as specified in the Schedule of Activities (Section 1.3) Instructions for the collection and handling of biological samples will be provided by the

sponsor. The actual date and time (24-hour clock time) of each sample will be recorded in the eCRF.

9. Statistical Considerations

9.1 Statistical Hypotheses

No formal statistical hypotheses will be tested.

9.2 Sample Size Determination

Up to 50 subjects will be enrolled in the study (approximately 10 subjects in a dose exploration phase and up to 40 subjects in a dose expansion phase). Additional subjects (up to 20) may be enrolled in 1 or more monotherapy dose levels that have

been shown to be safe and tolerable (defined as backfill enrollment). This backfill enrollment may be done to better estimate the RP2D and better characterize the safety, efficacy, PK, [REDACTED] of AMG 160 monotherapy and may be concurrent with dose escalation to identify the MTD.

An initial 2 to 4 subjects will be enrolled and treated with Dose Level 1 (1 dose level below RP2D of AMG 160 Study 20180101). Rules for dose-escalation/de-escalation are derived using an mTPI model with a target toxicity probability of 0.28 (see Section 6.2.1.1). If the dose is not tolerated (based on target DLT rate > 28%), the dose level will be reduced 1 level below the starting dose. Alternative dosing schedules, including further dose escalation as per the ongoing mCRPC trial (Study 20180101), may be explored based on emerging safety and PK data. The sample size in the dose exploration phase is based on practical consideration and is consistent with conventional oncology studies with the objective to estimate the MTD.

With 2 subjects in a cohort, there is a 19% to 55% probability of observing at least 1 DLT if the true DLT rate is 10% to 33% and with 4 subjects in a cohort, there is a 34% to 80% probability. With 6 subjects in a cohort, there is a 47% to 91% probability of observing at least 1 DLT if the true DLT rate is 10% to 33% and with 10 subjects in a cohort, there is a 65% to 98% probability.

In the dose expansion phase, a subject number of 40 will provide a 87% probability of observing at least 1 adverse event with 5% incidence rate. An exact 95% binomial CI will be provided for overall response rate. With the 40 subjects and 20% overall response rate, the expected 95% CI would be 9% to 36%.

9.3 Analysis Sets, Subgroups, and Covariates

9.3.1 Analysis Sets

The analysis of all endpoints, unless noted otherwise, will be conducted on the Safety Analysis Set defined as all subjects that are enrolled and receive at least 1 dose of AMG 160.

The analysis of DLT will be conducted on the DLT Analysis Set defined as all subjects that are enrolled and receive at least 1 dose of AMG 160 with an evaluable DLT endpoint. The DLT endpoint is evaluable if either: 1) the subject experiences a DLT; or 2) the subject does not experience a DLT after receiving all planned doses within the 28-day DLT window in cycle 1.

9.3.2 Covariates

The relationship between covariates and efficacy endpoints may be explored if appropriate.

9.3.4 Handling of Missing and Incomplete Data

Descriptive statistics will be used to identify the extent of missing data. Missing or incomplete dates that are critical to efficacy and safety analysis (eg, date of death, adverse event start date) will be imputed. Detailed imputation rules will be documented in statistical analysis plan.

9.4 Statistical Analyses

The statistical analysis plan will be developed and finalized before database lock. Below is a summary of the timing and methods for the planned statistical analyses. To preserve study integrity, the final analysis will be conducted and reported following the end of study, as defined in Section 4.4.1.

9.4.1 Planned Analyses

9.4.1.1 Interim Analysis and Early Stopping Guidelines

Safety data will be reviewed on an ongoing basis.

During dose exploration and formally during DLRMs, Amgen, in consultation with the site investigators, will review all available cumulative data by cohort prior to making dose escalation or dose de-escalation recommendations. Adverse events and DLTs observed in all subjects will be evaluated continually and fully integrated into all DLRMs and considered in all enrollment and dosing decisions. During dose expansion, Amgen will conduct evaluations of the ongoing grade 4 or higher treatment-related adverse event rate to assess if the threshold for possible early trial termination has been reached. If this threshold is met, enrollment to dose expansion will be halted pending review of safety data by the DLRT. After receiving the DLRT recommendation, Amgen will choose to take one of the following actions.

- 1) Terminate the trial

- 2) Amend the protocol to potentially improve the benefit/risk for subjects (eg, increase safety monitoring, modify dose/schedule, mandate [REDACTED])
- 3) Continue dose expansion without any changes

The stopping rules use a Bayesian approach proposed by Thall et al, 1995 to terminate the study if the posterior probability that the grade 4 or higher treatment-related adverse event rate is greater than 20% is $> 80\%$. The stopping boundaries assume a prior distribution of Beta (0.40, 1.60) are presented in [Table 9-1](#) and the operating characteristics with pre-specified batch size of 10 new subjects per batch are presented in [Table 9-2](#). The operating characteristics in [Table 9-2](#) provide the probability of stopping the trial early for given hypothetical true rate of grade 4 or higher treatment-related adverse events, whereas the stopping criteria in [Table 9-2](#) are based on situations where the empirical evidence would result in a posterior probability of $\geq 80\%$ that the true grade 4 or higher treatment-related adverse event rate is $\geq 20\%$.

Table 9-1. Stopping Boundary for Dose Expansion With Posterior Probability of 80% and Grade 4 or Higher Treatment-related Adverse Event Limit of 20%

Number of Subjects	Stop Study if Observing These Many Grade 4 or Higher Treatment-related Adverse Events
10	≥ 4
20	≥ 6
30	≥ 9
40	Dose Expansion Complete

Table 9-2. Operating Characteristics With Batch Size of 10 Subjects

True Grade 4 or Higher Treatment-related Adverse Event Rate	Probability of Early Stopping of Dose Expansion	Average Dose Expansion Sample Size
0.10	2.0%	39.5
0.15	9.1%	37.6
0.20	23.2%	33.9
0.25	42.2%	28.8
0.30	61.6%	23.4

A formal interim analysis of available safety and efficacy data will occur when the first 10 evaluable subjects enrolled have had the opportunity to complete 4 months on study. This interim analysis will estimate MTD, support the determination of RP2D, conduct futility analysis of objective response rate (ORR), and support the evaluation of benefit/risk profile of AMG 160 as a monotherapy.

[figure not shown]
A futility analysis of ORR will be performed using Bayesian predictive probability (Lee and Liu, 2008) when the first 10 evaluable subjects reach month 4. If the predictive probability of observing ORR response > 15% at the end of the study with 50 evaluable subjects is less than 30%, the study may stop early ($pT = 0.25$). Equivalently, if we observe ≥ 1 objective responder in the first 10 subjects, an additional subjects (up to 40) will be enrolled into the expansion cohort. The predictive probability is calculated with a noninformative prior, Jeffreys prior, Beta(0.5, 0.5).

Similarly, futility analyses will also be conducted during the expansion cohort. The stopping boundaries are presented in [Table 9-3](#). The operating characteristics in [Figure 9-1](#) provide the probability of stopping the trial early for given hypothetical true rate of ORR.

Table 9-3. Objective Response Rate Stopping Boundary

Number of Evaluable Subjects Each Month 4	Stop Study if Observed Objective Response Rate (ORR) Response
10	< 1
20	< 2
30	< 3
40	< 4
50	Study Complete

Figure 9-1. The Probability of Stopping The Trial Early

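### The dose-expansion safety boundary sets no minimum observation time for the subjects it counts, so a look taken at the 10th, 20th or 30th dosing halts less often than the fully observed rule

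*Protocol*

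**What the plan says.** Protocol Section 9.4.1.1 and SAP Section 7.1 carry the same text. "During dose expansion, Amgen will conduct evaluations of the ongoing grade 4 or higher treatment-related adverse event rate", and enrolment is halted for review by the Dose Level Review Team (DLRT) once the threshold is met. The threshold is a posterior probability above 80% that the rate exceeds 20%, under a Beta(0.40, 1.60) prior.

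Protocol Table 9-1 (SAP Table 7-1) gives the boundary as at least 4, 6 and 9 at 10, 20 and 30 subjects, with expansion complete at 40. The count column is headed "Stop Study if Observing These Many Grade 4 or Higher Treatment-related Adverse Events"; the other column is only a number of subjects. Table 9-2 (SAP Table 7-2) gives "operating characteristics with pre-specified batch size of 10 new subjects per batch".

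No observation period, event window or evaluability rule is attached to this boundary. The default population in protocol Section 9.3.1 is the "Safety Analysis Set defined as all subjects that are enrolled and receive at least 1 dose of AMG 160".

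Two other rules do state follow-up. The response boundary in Table 9-3 is indexed by "Number of Evaluable Subjects Each Month 4", and the DLT Analysis Set in Section 9.3.1 requires either a DLT or all planned doses within the 28-day window.

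**The concern.** A Beta-binomial posterior on r events in n subjects assumes that each of the n has had the full chance to show an event. Enrolment continues between looks. If the look falls when the 10th subject is dosed, that subject has no observed time and the few before have little, yet each counts as a complete non-event. At any given look this can only lower the count. The effect is largest at the first look, where the denominator is smallest and a halt would spare the most subjects. The Table 9-2 operating characteristics would then describe a rule different from the one applied.

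**Working it through.** **1. Reproduce the boundary.** Find the smallest r with Pr(p > 0.20 | Beta(0.4 + r, 1.6 + n − r)) > 0.80.

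- n = 10: 0.895 at r = 4, 0.719 at r = 3.
- n = 20: 0.826 at r = 6, 0.666 at r = 5.
- n = 30: 0.885 at r = 9, 0.783 at r = 8.

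Table 9-1 is confirmed.

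**2. Reproduce Table 9-2.** Exact sequential binomial recursion, every subject fully observed, maximum 40.

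| True rate | Printed stop % | Looks at 10, 20, 30 | Looks at 10, 20 only | Printed average N | Average N, three looks |
|---|---|---|---|---|---|
| 0.10 | 2.0 | 2.05 | 2.00 | 39.5 | 39.5 |
| 0.15 | 9.1 | 9.7 | 9.08 | 37.6 | 37.6 |
| 0.20 | 23.2 | 25.8 | 23.18 | 33.9 | 33.9 |
| 0.25 | 42.2 | 47.7 | 42.17 | 28.8 | 28.8 |
| 0.30 | 61.6 | 69.2 | 61.64 | 23.4 | 23.4 |

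The average-N column uses all three looks. The probability column matches only if the look at 30 is left out; two looks would give an average N of about 34.2 at 0.20 and 24.2 at 0.30. The benchmark for what follows is therefore the fully observed three-look rule. At 0.30 its stopping probabilities are 35.0% at n = 10, 26.6% at n = 20 and 7.6% at n = 30, total 69.2%.

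**3. Size of the dilution.** Neither accrual nor onset is in the documents. Assumptions: Poisson accrual of a subjects per 28 days; onset uniform over W days from first dose; one event per affected subject; each look at the dosing of subject 10, 20 or 30; late events counted at the next look.

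The expected number of wholly unobserved subject-equivalents at a look is about m = 1 + a × W / (2 × 28): the subject just dosed, plus half of those dosed in the last W days. For W = 28, m = 2, 3 and 4 at a = 2, 4 and 6. The ratio of observed to true rate is 1 − m/n:

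- n = 10: 0.80, 0.70, 0.60.
- n = 20: 0.90, 0.85, 0.80.
- n = 30: 0.93, 0.90, 0.87.

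**4. Effect on halting.** Simulation, 200,000 trials per setting, true rate 0.30.

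| Onset window, accrual per 28 days | Halt at n = 10 | Halt by n = 30 | Average N |
|---|---|---|---|
| Fully observed | 35.0% | 69.2% | 23.4 |
| 3 days, 2 / 4 / 6 | 26 / 25 / 25% | 63 / 63 / 62% | 25.6 / 25.8 / 26.0 |
| 10 days, 2 / 4 / 6 | 24 / 22 / 19% | 62 / 60 / 58% | 26.1 / 26.7 / 27.4 |
| 28 days, 2 / 4 / 6 | 20 / 14 / 9% | 59 / 53 / 48% | 27.2 / 29.1 / 30.7 |

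Repeat runs differ by less than one percentage point, so the ranges quoted elsewhere are rounded outwards. At a true rate of 0.20, overall halting is 12–21% over the same settings, against 25.8% fully observed.

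**5. Check of a repair.** Waiting until the last of the fixed first 10, 20 or 30 subjects reaches day 28, with onset within 28 days, returns 35% at the first look and 69% overall at 0.30.

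**The case against.** Several points on the other side have force.

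- **The size is assumed.** Accrual, onset and the exact moment of a look are not stated, and the plan calls the evaluations ongoing. Early onset is plausible: protocol Section 11.10.1 places the raised risk of cytokine release syndrome in the first few days after administration. That shrinks the effect but does not remove it: even with onset within 3 days, first-look halting is about 25% rather than 35%.
- **There is a separate safeguard.** Protocol Section 6.2.2.1 suspends accrual, pending a safety analysis and FDA review, after any one related grade 5 event or any two of the same clinically significant related grade 4 events. It has no denominator to dilute. It does not cover differing grade 4 events, which a pooled rate is meant to detect.
- **Late events are not lost.** They count at the next look, and the simulation includes this. After 30 there is no further boundary.
- **Counting events could push the other way.** The column heading counts adverse events, so one subject with several could bring a halt forward.

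Three stronger readings are tempting and should not be drawn. First, a reader might infer that the rule stops less often than the printed Table 9-2 probabilities. Those omit the look at 30, so they are too low a benchmark: at 0.30 with 3-day onset the diluted rule still stops 62–64% of the time, against 61.6% printed. Second, enrolled but undosed subjects do not dilute the rate, because the default analysis set requires a dose. Third, this is not the only monitored rate without follow-up: the siltuximab boundaries (protocol Section 9.4.1.1.1, SAP Section 7.1.1) have none either.

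**Conclusion.** The point stands as a gap in the definition of a subject-protection rule. Table 9-1 and SAP Table 7-1 do not say how long a counted subject must have been observed, while the posterior and the operating characteristics assume full observation. For looks taken at the 10th, 20th and 30th dosing, halting is less frequent than under the fully observed rule in every setting run.

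At a true rate of 0.30, with assumed accrual of 2 to 6 per 28 days and onset uniform over 3 to 28 days, first-look halting is 9–26% instead of 35%, overall halting 47–64% instead of 69%, and average N 25.5–30.7 instead of 23.4. The printed average-N column is a sound comparator because it reproduces with three fully observed looks. The direction at a given look does not depend on the assumptions; the size does. If evaluations between looks were truly continuous the loss would be smaller, but the plan does not say so and Table 9-2 assumes batches of 10.

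**What to change.** In protocol Section 9.4.1.1 and SAP Section 7.1:

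- Apply each boundary to a fixed set: the first 10, 20 and 30 dosed expansion subjects.
- Hold the formal look when the last subject of that set completes a stated observation period; 28 days would match the plan's DLT window.
- Halt at once if the boundary count within that set is reached sooner.
- State that subjects with at least one qualifying event are counted, not events.
- Recompute the Table 9-2 (SAP Table 7-2) probability column over all three looks: 2.0 (2.05 before rounding), 9.7, 25.8, 47.7 and 69.2% at true rates 0.10, 0.15, 0.20, 0.25 and 0.30. The average-N column can stay.

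Do not define the denominator as subjects with 28 days or an earlier event. That admits recent subjects only if they have had an event and biases the rate upward. Under 28-day onset and accrual of 2, 4 and 6 per 28 days, stopping at a true rate of exactly 0.20 rises from 25.8% to about 29, 33 and 37%.

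The cost is wording and one recomputed column, with no added procedures. The formal look comes about four weeks later, and some subjects may be enrolled meanwhile (2 to 6 at the assumed accrual); the immediate halt limits this.
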